	Subjects who are positive for POC-CCA test will provide stool samples to assess infection intensity using the Kato-Katz method. Kato-Katz diagnosis of S. mansoni infection: two stool samples will be collected from each subject on different days within a maximum of five days, at day -28 to day -1 as baseline and 14-21 days after dosing (for treatment efficacy assessment). Three Kato-Katz thick smears (41.7 mg) will be prepared from each stool sample and read under a microscope following the instructions of the Kato-Katz manual from the World Health Organization. Infection intensity (expressed as egg count per gram of stool (epg)) will be calculated for each individual. S. mansoni positive diagnosis is defined as positive egg counts of S. mansoni in stool (>1 egg/1 occasion) according to the WHO classification: light (1-99 eggs per gram of faeces), moderate (100-399 eggs per gram of faeces) and heavy (≥ 400 eggs per gram of faeces) infections. Subjects will be tested for S. haematobium in order to exclude S. mansoni/S. haematobium co-infections. Diagnosis of S. haematobium infection will be made by urine examination using the filtration technique. One urine sample will be collected from each subject at day -28 to day -1 .10 ml of urine samples will be filtered through a filter mesh which will be then examined under the microscope for S. haematobium egg count. S. haematobium positive diagnosis is defined as positive egg counts of S. haematobium in urine (>1 egg/10 ml of urine).			

Eligibility criteria

To be eligible for the study, subjects must meet all of the inclusion criteria and none of the exclusion criteria.

Inclusion criteria

- Written informed consent from one of the parents/legal representatives prior to any trial related procedure
- Male and female children aged 2 to 6 years (Part 1) and 3 to 24 months (Part 2)
- S. mansoni positive diagnosis defined as positive egg counts in stool (>1 egg/1 occasion) according to WHO classification [1]: light (1-99 eggs per gram of faeces), moderate (100-399 eggs per gram of faeces) and heavy (≥400 eggs per gram of faeces) infections
- Minimum weight of 8.0 kg in 2- to 6-year-old children and of 4.0 kg in 3- to 24-month infants
- Parent/legal representative's ability to communicate well with the Investigator, to understand the protocol requirements and restrictions, and willing their children to comply with the requirements of the entire trial, i.e.:

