7.1.3 Treatment period

Treatment period will last 1 day. Subjects will be hospitalized from the morning of dosing until at least 24 hours after IMP administration. During this time, subjects will be monitored for AEs.

Pre-dose assessments

Subjects will undergo physical examination, vital signs assessment and re-check of eligibility criteria. If assessments have been done on the same day they do not need to be repeated.

Post-dose assessments

Vital signs will be recorded 8 hours after first dosing. Physical examination will be performed 8 and 24 hours (\pm 10% IN HOURS) after first dosing.

Clinical safety laboratory evaluations (i.e. hematology, biochemistry and urinalysis) and urine collection for POC-CCA test will be performed 24 hours (± 10% in hours) after dosing. All biological assessments will be performed in fasting condition, if possible.

In case the participant, due to logistical or social reasons will have to spend an additional night in the hospital, the end of confinement will be documented after the specified 18/24 Hours and the

additional night will not be considered as part of confinement. As such, it will not qualify as SAE, as described in section 7.4.1.1.

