7.1.4 Follow-up visit

Follow-up visits will take place as specified in APPENDIX II.

During the 3 days following their release from the hospital, subjects will be monitored by the nurses in the health areas and/or by the community agents of the different localities for potential adverse events. If an AE is observed, the latter need to inform the medical team in charge of the study for the necessary follow up.

At day 8 (+/- 1 day), urine samples will be collected for the POC-CCA test. If an AE related to liver function occurs before hospital discharge (within 24 hours after dosing), the subject will be further monitored by the study team in the villages and an additional blood sample will be collected at Day 8 for biochemistry evaluation.

At the End of Study visit (between day 14 and 21), subjects will be asked to provide stool and urine samples for Kato-Katz method and POC-CCA test. The following tests and information gathering will be also performed:

Vital signs in supine position including:

- Blood pressure (systolic and diastolic) to be assessed at least 5 minutes after resting
- Pulse rate to be assessed at least 5 minutes after resting
- Body temperature

Complete physical examination

If a subject withdraws prematurely from the trial, every effort will be made to undertake a final examination visit as soon as possible and perform all procedures of the End of Study visit.

Any ongoing medically relevant abnormal findings at the End of Study visit, including safety laboratory tests, will be followed up until resolution or stabilization (according to Section 7.4.1.6)

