7.3 Efficacy Assessments

7.3.1 Assessment of primary efficacy endpoint

Egg counts in the stools (expressed as egg count per gram of stool (epg) 14-21 days after treatment as determined by Kato-Katz method. Two stool samples will be collected from each subject on different days within a maximum of 5 days, at screening and 14-21 days after treatment. Three Kato-Katz thick smears will be prepared from each stool sample and read under the microscope.

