Kato-Katz diagnosis of S. mansoni infection : two stool samples will be collected from each subject on different days within a maximum of five days, at screening, as baseline and 14-21 days after dosing (for treatment efficacy assessment). Three Kato-Katz thick smears (41.7 mg) will be prepared from each stool sample and read under a microscope following the instructions of the Kato-Katz manual from the World Health Organization. Infection intensity (expressed as egg count per gram of stool (epg)) will be calculated for each. S. mansoni positive diagnosis is defined as positive egg counts of S. mansoni in stool (>1 egg/1 occasion) according to the WHO classification: light (1-99 eggs per gram of faeces), moderate (100-399 mg eggs per gram of faeces) and heavy ( $\geq$ 400 eggs per gram of faeces) infections.
Diagnosis of S. haematobium infection will be made by urine examination using the filtration technique. One urine sample will be collected from each subject at screening. 10 ml of urine samples will be filtered through a filter mesh which will be then examined under the microscope for S. haematobium egg count. S. haematobium positive diagnosis is defined as positive egg counts of S. haematobium in urine (1 egg/10 ml of urine).

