## **16.2.2Egg reduction**

#### Analysis set(s):

• Primary analyses will be based on the mITT and PP analysis sets.

The group/collective egg reduction rate will be determined as follows:

- ERRA (%) = relative difference expressed in percent between the post-treatment mean egg count and the pre-treatment mean egg count ((pre-treatment egg count - post-treatment egg count) / pre-treatment egg count) including all patients.
- $ERR_G$  (%) = relative difference expressed in percent between the log-transformed posttreatment mean egg count and the log-transformed pre-treatment mean egg count ((logtransformed pre-treatment egg count - log-transformed post-treatment egg count) / logtransformed pre-treatment egg count) including all patients.
  - The following log transformation will be used to calculate the geometric mean: log(x + 1)

This log transformation is required, otherwise the ERRG result would only be calculated on uncured patients only, which would introduce a bias and an important underestimation of the true ERRG.

All raw egg counts will be multiplied by four prior to use in any derivation. Missing egg counts will be imputed using the LOCF approach.

To prepare the original data for bootstrapping, missing data will be imputed, followed by random sampling of pairs (2-tuples) of baseline and end-of-study egg counts, i.e. {Kato-KatzBaseline; Kato-KatzEnd-of-Study}, using PROC SURVEYSELECT, with unrestricted random sampling, at a sampling rate of 1 and 10 000 replicates. ERRA and ERRG will be computed by *replicate*, to establish the bootstrap sample.

The arithmetic mean of the bootstrap sample will constitute the point estimate. Corresponding 95% CIs will be determined using the percentile method, based on the bootstrap sample. Point and interval estimates of  $ERR_A$  and  $ERR_G$  will be presented by cohort. Mean Kato-Katz egg counts will be listed by cohort and subject and time point. Estimates of  $ERR_A$  and  $ERR_G$  will be presented graphically in the form of boxplots, by cohort.

The  $ERR_A$  or  $ERR_G$  slopes by treatment group will be compared to determine which treatment has the fastest egg clearance rate.

Results will be presented for each analysis set.

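### SAP 16.2.2 compares egg-reduction slopes to name the fastest egg clearance, but egg counts are scheduled at only two occasions, so any slope is a two-point average that cannot show speed

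*SAP*

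**What the plan says.** SAP 16.2.2 (Egg reduction) defines a group ERR from arithmetic means and another from log-transformed counts. After describing the bootstrap and the displays, it adds that the ERR "slopes by treatment group will be compared to determine which treatment has the fastest egg clearance rate". No slope formula, time axis, model or test follows.

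The counts behind ERR come from two occasions:

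- Protocol 7.3.1 has two stool samples collected "on different days within a maximum of 5 days, at screening and 14-21 days after treatment".
- SAP 6.2 (Diagnosis) places them "at screening, as baseline and 14-21 days after dosing (for treatment efficacy assessment").
- The bootstrap in SAP 16.2.2 resamples pairs, described as "2-tuples) of baseline and end-of-study egg counts".
- The Protocol Appendix II schedules for C1, C2-C7 and C8-C9 mark Kato-Katz only at pre-screening and End of Study. The Appendix III volume tables list stool only at those two visits.

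Between those occasions the efficacy sample is urine. Protocol 7.1.3 states that "urine collection for POC-CCA test will be performed 24 hours" after dosing, and Protocol 7.1.4 states that at Day 8 "urine samples will be collected for the POC-CCA test".

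One text points the other way. The inclusion criteria (Protocol Synopsis and 5.3.1) require willingness to give stool as well as urine at 24 hours and at 8 days.

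Protocol 8.5.3 defines ERR as a ratio of two means and contains no slope analysis. SAP section 9 nevertheless reports that the protocol's statistical methods were adopted.

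**The concern.** Speed of clearance is a statement about the path of egg counts over time. With one count before dosing and one two to three weeks after, that path is not observed. The sentence promises a conclusion, namely which treatment is fastest, that the planned data cannot deliver. Because the method is undefined, the slope would also have to be invented at analysis, possibly with results in view.

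The stake is an unsupported statement in the report. SAP section 5 says its results go into the clinical study report and may go into submissions or manuscripts. SAP 8.2 has the secondary endpoints analysed at the end of Part 1 and the results shared with the Safety Monitoring Committee. A claim of fastest egg clearance would read as a property of the formulation or dose.

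**Working it through.** The plan gives no figure for the slope, so there is none to reproduce. The check is a count of time points, followed by what a slope could mean with that many.

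**1. Egg-count occasions per child** (Protocol Appendices II and III, 7.1.3, 7.1.4, 7.3.1; SAP 6.2, 16.2.1, 16.2.2)

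| Visit | Kato-Katz | POC-CCA (urine) |
|---|---|---|
| Pre-screening, D-28 to D-1 | yes | yes |
| D2 | no | yes |
| D8 | no | yes |
| End of Study, D14-D21 | yes | yes |

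There are two occasions, one of them after treatment. POC-CCA is an antigen score (negative to 3+), not an egg count. The two stools per occasion, three smears each, form one assessment. Carrying the last observation forward adds no time point: the only earlier count is baseline, so that child's reduction is zero.

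**2. Slope over a common nominal interval T**

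Linear: slope = ERR/T. Log: slope = -ln(1 - ERR)/T. Both rise with ERR when T is fixed, so arms are ranked exactly as by ERR.

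**3. Slope over actual days, same 90% reduction** (the 90% is an assumption; SAP section 11 defines no Day 0 and gives the End of Study window as Day 14 to 21, +3)

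| Baseline to End of Study | Days | Points per day (90/days) | Log scale (ln 10/days) |
|---|---|---|---|
| D-1 to D14 | 14 | 6.43 | 0.164 |
| D-1 to D21 | 21 | 4.29 | 0.110 |
| D-28 to D21 | 48 | 1.88 | 0.048 |
| D-28 to D24 | 51 | 1.76 | 0.045 |

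Day 14 against Day 21 gives 21/14 = 1.5. The extreme intervals give 51/14 = 3.6. Both are contrasts between individual children with identical reductions.

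**4. Different speeds, same two-point slope** (assumed baseline 200 epg; t in days from dosing)

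| Assumed course | t=0 | t=1 | t=7 | t=14 |
|---|---|---|---|---|
| Fast, then plateau: 20 + 180·exp(-1.5t) | 200 | 60 | 20 | 20 |
| Steady: 200·exp(-(ln 10/14)t) | 200 | 170 | 63 | 20 |
| Late: flat to day 7, then 200·exp(-(ln 10/7)(t-7)) | 200 | 200 | 200 | 20 |

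Each gives ERR = 100 × (1 - 20/200) = 90% and slope = 90/14 = 6.43 points per day. The planned counts cannot separate them.

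**5. Cured children on the SAP's log(x + 1) scale** (natural log assumed)

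With zero eggs at follow-up, the slope over 14 days is ln(baseline + 1)/14. That is ln(25)/14 = 0.23 per day at 24 epg and ln(401)/14 = 0.43 per day at 400 epg. The difference reflects baseline burden alone.

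**The case against.** **Two points do give a rate.** This stands as far as it goes: an average change over the interval can be calculated. A reader might infer that no rate of any kind is estimable, and that is too strong. The limit is that the average carries nothing about speed beyond ERR and visit timing.

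**Visit timing need not enter.** The SAP does not say that actual days would be used. Under nominal times every arm has the same denominator and there is no timing distortion. This stands too, but the slope is then ERR under another name and the word fastest is a mislabel.

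**Timing should balance across arms.** A reader might take the factor of 1.5 as a possible bias between treatments. The documents do not support that. Part 1 is randomised, the arms share one visit window, and nothing suggests that the assessment day differs by arm. A distortion of that size would need one whole arm seen at Day 14 and another at Day 21.

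**The inclusion criteria mention stool at 24 hours and 8 days.** This is the one text that suggests serial stool data. No schedule, volume table or analysis turns it into an egg count, so it does not rescue the slope.

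**Nothing important depends on it.** Largely right. A reader might infer that the slope steers dose selection. The stated efficacy criterion is an observed cure rate above 70% (Protocol 8.1, SAP 7.1), and no text feeds the slope into that choice, the primary endpoint or the sample size.

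**Conclusion.** The slope sentence is wrong as written: comparing ERR slopes cannot determine which treatment clears eggs fastest. This rests on the count of scheduled egg assessments, two per child, and not on the illustrative numbers. The 90% reduction, the 200 epg baseline and the three time courses are assumptions chosen to show the mechanism; the factors of 1.5 and 3.6 apply to individuals and only if actual days are used.

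The consequence is an unsupported statement in a secondary, exploratory, descriptive analysis. The ERR estimates, their bootstrap intervals and the primary cure rate are unaffected by this point.

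**What to change.** Delete the slope sentence from SAP 16.2.2 and make no statement about speed of egg clearance. This alone removes the defect, since both ERRs with bootstrap intervals are already planned by cohort. The cost is one SAP edit.

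If an arm comparison is wanted, state it as a descriptive difference in ERR between each other Part 1 arm and the reference arm that SAP 10.2.1 already names (Biltricide 40 mg/kg single dose). That is six differences if C7 is included (7 - 1) and five if not. Percentile 95% CIs can be derived from the 10,000 replicates per cohort, provided that resampling is done within cohort. These differences are a small new derivation and need minor extra programming. Before ERR_G differences are reported, its formula should be checked, because SAP 16.2.2 writes it as a relative difference of log-transformed counts.

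Reconcile the inclusion criterion on stool at 24 hours and 8 days with the schedules and volume tables. If the comparison is kept in any form, record it in SAP section 9 as an addition to Protocol 8.5.3.

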## 16.3 Other Endpoint Analyses

## 16.3.1 Analysis for PK Endpoints

Due to technical challenges in the preparation of the PK samples, the planned PK analysis may be abandoned, in which case the data will only be listed.

## 16.3.2 PK/PD Correlation/Association

Continuous data:

The Pearson correlation coefficient between individual egg reduction rates (ERR) and the following will be calculated and presented in summary tables and scatterplots:

- Dose exposure (as described in section 15)
- Actual dose

Pearson correlation coefficients and plots will be presented separately for each treatment administered, i.e.:

- Biltiricide®
- rac-PZQ ODT
- L-PZQ ODT

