5.3.1 Inclusion Criteria

For inclusion in the study, all of the following inclusion criteria must be fulfilled:

- Written informed consent from one of the parents/legal representatives prior to any trial related procedure
- Male and female children aged 2 to 6 years (Part 1) and 3 to 24 months (Part 2)
- *S. mansoni* positive diagnosis, defined as positive egg counts in stool (>1 egg/1 occasion) according to WHO classification [1]: light (1-99 eggs per gram of faeces), moderate (100-399 eggs per gram of faeces) and heavy (≥400 eggs per gram of faeces) infections
- Minimum weight of 8.0 kg in 2- to 6-year-old children and of 4.0 kg in 3- to 24-month infants
- Parent/legal representative ability to communicate well with the Investigator, to understand the protocol requirements and restrictions, and willing their children to comply with the requirements of the entire trial, i.e.:
 - To be examined by a study physician at screening and 14-21 days after treatment
 - To provide stool and urine samples at day -28 to day -1, 24 h and 8 days after treatment, as well as 14-21 days after treatment
 - To provide venous blood samples for safety assessments

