8.3 Endpoints

8.3.1 Primary Endpoints

Clinical cure defined as no parasite eggs in the stools 14-21 days after treatment. Egg counts will be determined by Kato-Katz method. Cure rate will be calculated for each treatment arm as the percentage of subjects becoming egg-negative 14-21 days after treatment.

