## List of Abbreviations and Definition of Terms

AE	Adverse Event
AIDS	Acquired Immunodeficiency Syndrome
ALT	Alanine Aminotransferase
ANOVA	Analysis of Variance
AST	Aspartate Aminotransferase
ATC	Anatomical Therapeutic Chemical
$AUC_{0-\infty}$	Area under the concentration-time curve (AUC) from time zero to infinity
AUC 0-t	Area under the concentration-time curve (AUC) from time zero to the last sampling time at which the concentration is at or above the lower limit of quantification
AUC extra	Extrapolated AUC from time $t_{\text{last}}$ to infinity given as percentage from $AUC_{0\text{-}\infty}$
CL/f	Apparent total body clearance of drug
Cmax	Maximum observed concentration
CNER	Comité National d'Ethique et de la Recherche
CRF	Case Report Form
CRP	C-reactive Protein
CSR	Clinical Study Report
ERR	Individual Egg Reduction Rates
ERRA	Group/Collective Egg Reduction Rate (based on arithmetic mean)
ERR G	Group/Collective Egg Reduction Rate (based on geometric mean)
ICH	International Conference on Harmonisation
IMP	Investigational Medicinal Product
PPD	PPD
LLN	Lower Limit of Normal
LOCF	Last Observation Carried Forward
LSLV	Last subject, last visit
MedDRA	Medical Dictionary for Regulatory Activities
mITT	Modified Intention-to-Treat
NCA	Non-compartmental Analysis

NCI-CTCAE	National Cancer Institute – Common Terminology Criteria for Adverse
	Events
ODT	Oral dispersible tablets
PD	Pharmacodynamic(s)
РК	Pharmacokinetic(s)
РР	Per Protocol
РТ	Preferred term
PZQ	Praziquantel
Q1	First quartile
Q3	Third quartile
SAE	Serious Adverse Event
SAF	Safety Analysis Set
SAP	Statistical Analysis Plan
SCI	Schistosomiasis Control Initiative
SD	Standard deviation
SERU	Scientific and Ethics Review Unit
SDTM	Standard Data Tabulation Model
SMC	Safety Monitoring Committee
SOC	System Organ Class
t½	Apparent terminal half-life
TEAE	Treatment Emergent Adverse Event
t.i.d.	Three times a day
tlag	Time prior to the first measurable (non-zero) concentration
TLF	Tables, Listings, and Figures
ULN	Upper Limit of Normal
tmax	Time to reach the maximum concentration
Vz/f	Apparent volume of distribution during the terminal phase
λz	Apparent terminal elimination rate constant

4 Modification History			
Unique Identifier for SAP Version	Date of SAP Version	Author	Changes from the Previous Version
1.0	01 Aug 2016	PPD	N/A

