## 7 Sample Size/Randomisation

## 7.1 Sample Size

Part 1: this study is exploratory. There is no hypothesis testing.

The sample size is based on the minimum number of subjects to reach a meaningful precision of the primary efficacy endpoint estimate (cure rate) in each arm, considering the stratification factor.

There are limited historical data on the impact of the severity of infection on the observed cure rate. In the recent study by Keiser et al. (unpublished data), the observed cure rate in *S. mansoni* infected children varied between 55% and 60% in moderately infected children and 70% and 85% in light infected children depending on the dose. The table below presents the overall cure rate projections according to different assumptions of true cure rate in mild (low) and moderately infected children.

Overall cure rate (95%CI),	Assump	tions of Cure F	Rate in Light In	fections
(N=50)	70%	75%	80%	85%

	50%	62% (48%, 74%)	65% (52%, 78%)	68% (56%, 80%)	71% (60%, 82%)
Assumptions of	55%	64%	67%	70%	73%
Cure Rate in		(50%, 76%)	(54%, 80%)	(58%, 82%)	(62%, 84%)
Moderate/Heavy	60%	66%	69%	72%	75%
Infections		(52%, 78%)	(56%, 80%)	(60%, 84%)	(64%, 86%)
	65%	68% (54%, 80%)	71% (58%, 82%)	74% (62%, 86%)	77% (66%, 88%)

A minimum-clinical meaningful cure rate is considered as equal to 70%. With 50 evaluable patients enrolled, stratified as 40% moderate/heavy and 60% light, the corresponding 95% CI lower bound of an observed cure rate of 70% would be above ~58%, depending on potential difference between the strata. This sample size would also provide the minimum number of subjects to estimate the cure rate within strata.

Considering the efficacy criteria for the selection of the dose (observed cure rate >70%), through simulations, the table below presents the probability of observing an overall cure rate >= 70% based on different scenarios of true cure rates based on different strata, assuming a stratification of 40% moderate/heavy infections and 60% light infections.

Probability of observ	ring a	Assumptio	ns of Cure I	Rate in Ligh	t Infections
cure rate $\geq 70\%$ , N	=50,	70%	75%	80%	85%
	50%	15%	27%	45%	64%
Assumptions of Cure Rate in	55%	23%	38%	57%	76%
Moderate/Heavy Infections	60%	33%	51%	70%	85%
intections	65%	45%	63%	80%	92%

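### SAP 16.3.2 relates dose to individual egg reduction only through Pearson's r, which a few uncured children dominate; a rank coefficient and a stated formula would cost almost nothing.

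*SAP*

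**What the plan says.** SAP 16.3.2 (PK/PD Correlation/Association) plans "The Pearson correlation coefficient between individual egg reduction rates (ERR") and two dose measures: exposure as derived in SAP 15, and actual dose. On grouping it says: "Pearson correlation coefficients and plots will be presented separately for each treatment administered". The groups are Biltricide (two arms), rac-PZQ ODT (two arms) and L-PZQ ODT (up to three arms). Results go into summary tables and scatterplots. No rank coefficient, transformation, lower limit or outlier rule is given.

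The variable itself is not defined. The SAP's abbreviation list expands ERR as "Individual Egg Reduction Rates", but SAP 16.2.2 gives formulas only for the two group rates. There, log(x + 1) is used for the geometric group rate and LOCF for missing counts. SAP 16.3.2 repeats neither. SAP 11 states a general default of not replacing missing data unless otherwise specified.

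Protocol 8.3.1 defines the primary endpoint: "Clinical cure defined as no parasite eggs in the stools 14-21 days after treatment". SAP 7.1 says "A minimum-clinical meaningful cure rate is considered as equal to 70"%.

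**The concern.** A cured child has a post-treatment count of zero and therefore an individual ERR of exactly 100%, whatever the baseline. The variable has a large spike at its maximum and a left tail made up only of uncured children. Eligibility requires just "positive egg counts in stool (>1 egg/1 occasion"), and 60% of children are planned to have light infections. Baseline counts can therefore be very small, and a modest rise in eggs can give a strongly negative percentage.

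Pearson's r weights values by their distance from the mean, so it is a poor summary of a dose trend in such a variable. Dose-response is a secondary objective (Protocol 4.2). After PK sampling was dropped, Protocol 5.2 bases the evaluation on cure rate and egg reduction against dose. This is the only planned coefficient that relates each child's egg reduction to dose.

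**Working it through.** **1. The plan's own figure.** The documents give no figure for this correlation. The nearest is the probability of about 85% of observing a cure rate of at least 70%, with 30 light infections at 85% and 20 moderate/heavy at 60%. The exact sum of Binomial(30, 0.85) and Binomial(20, 0.60), P(X ≥ 35), is 84.7%. The simple Binomial(50, 0.75) gives 83.7%. The figure reproduces, so its cure rates and severity mix are used below.

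**2. Share of children at exactly 100%.** SAP 7.1 works "assuming a stratification of 40% moderate/heavy infections and 60% light infections". It cites cure rates that "varied between 55% and 60% in moderately infected children and 70% and 85% in light infected children depending on the dose", and its grid spans 50–65% and 70–85%.
- Lowest cell: 0.6 × 70% + 0.4 × 50% = 62%.
- Highest cell: 0.6 × 85% + 0.4 × 65% = 77%.

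So 62–77% of children are expected to tie at 100%.

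**3. What Pearson's r then measures.** Let d be dose and E individual ERR. Because Σ(d − d̄) = 0,

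Σ(d − d̄)(E − Ē) = Σ(d − d̄)(E − 100).

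Every cured child contributes zero to the right-hand side. The numerator of r is therefore a sum over uncured children only, each weighted by 100 − E. A numerical check gave 14459.77 on both sides.

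**4. Size of one weight.** Assume E = 100 × (1 − post/pre). With the SAP's multiplier of four, a child going from 2 to 10 raw eggs goes from 8 to 40 epg: E = 100 × (1 − 5) = −400%, a shortfall of 500. A child with an 80% reduction has a shortfall of 20. At the same dose the first child counts 500/20 = 25 times as much.

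**5. Simulation at cure rates in the documents' range.** Inputs: 50 per arm, 60% light and 40% moderate/heavy, 600 runs per scenario. Assumptions not in the documents:
- Baseline is log-uniform on 8–99 and 100–1500 epg.
- Mean post-treatment count in uncured children is 20%, 50% or 80% of baseline, negative binomial with k = 0.5 or 2.
- Actual mg/kg dose scatters by about 10%.

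About 70% of values sat at 100%, and skewness ran from −2.4 to −4.1. The three lowest of 100–150 children carried 34–68% of the ERR sum of squares.

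**6. Comparison of coefficients.** Same range for uncured counts (mean 20–80% of baseline), about 70% of values at 100%, two-sided 5% level for detection:

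| Result | Pearson | Spearman |
|---|---|---|
| Cure 60% to 80%: trend detected | 19–34% | 45–54% |
| Cure 60% to 80%: sign flips when two lowest ERRs dropped | 5–14% | 1–2% |
| Nearly flat trend: sign flips when two lowest ERRs dropped | 17–28% | 8–10% |

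The median lowest ERR ran from about +32% to about −383%, depending on the assumed counts.

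**7. Missing counts.** Under LOCF a missing post-treatment count takes the baseline value: ERR = 100 × (1 − 1) = 0%. With 17% such children and 60 per arm, a second spike appears at 0%, and the share carried by the three lowest falls to about 33%. Whether SAP 16.3.2 uses LOCF therefore changes the distribution.

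**The case against.** **The negative tail is assumed.** No document gives post-treatment counts in uncured children, and the unbounded formula is an inference. This stands: a reader might infer a long negative tail as a fact, but under some assumptions the lowest ERR is positive. The spike at 100%, the left skew and the weighting by shortfall remain in either case.

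**Detection rates are a harsh yardstick.** SAP 16.3.2 plans no test or decision on this coefficient, SAP 11 calls all tests exploratory, and the scatterplots would show extreme children. This stands as a limit on consequence. The rates in step 6 show relative stability, not lost power for a planned test.

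**Dose-response is covered elsewhere.** A reader might infer that a few children decide the trial's dose conclusion. The documents do not support that. The stated efficacy criterion is an observed cure rate above 70%. Dose-response for cure is examined by logistic regression and dose-response curves (SAP 16.1.2) and by Mantel-Haenszel trend tests (SAP 16.3.2). Group egg reduction is given by cohort with bootstrap intervals (SAP 16.2.2). None of these uses individual ERR.

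**Spearman adds little.** With about 70% ties, it mostly ranks cured against not cured: its correlation across runs with the same coefficient computed on cure alone was about 0.96–0.98. In a similar simulation the planned trend test detected the 60% to 80% rise in 57–61% of runs, against 43–54% for Spearman and 19–36% for Pearson. This stands, and it is a reason to keep Pearson beside Spearman. It does not make Pearson a sound sole coefficient.

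**Conclusion.** The point holds as a minor, nearly free improvement. The ties at 100% and the dependence of r on uncured children's shortfalls follow from the definition of cure, given the usual percentage reduction for each child. With about 70% of children cured, Pearson detects the assumed trend roughly half as often as Spearman (19–34% against 45–54%), and its sign is less stable when two children are removed. These sizes rest on assumed baseline and post-treatment counts, and the depth of the tail cannot be known from the documents. Dose selection and the cure-based dose-response results are not put at risk. The more basic gap is that individual ERR has no stated formula or missing-data rule.

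**What to change.** In SAP 16.3.2:
- Report Spearman's rank correlation, with average ranks for ties, as the main coefficient in the same tables and plots. Keep Pearson beside it if wanted, as a summary sensitive to the size of the reduction.
- State the individual ERR formula, for example 100 × (1 − post/pre).
- State whether LOCF from SAP 16.2.2 applies and, if so, that it sets a child with a missing post-treatment count to ERR = 0%.

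The cost is a few lines of SAP text and one procedure option; no new data are needed. The downside is that, with so many ties, Spearman will say little about the size of the reduction beyond what the trend test on cure already shows.
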